In subjects with TS, ecopipam has been evaluated in two studies, one study in adult subjects with TS and one study in children/adolescents with TS. In the pediatric TS study, overall, adverse events were more common in ecopipam compared to placebo. There were no serious adverse events (SAEs) and only one subject discontinued treatment due to an adverse event in the ecopipam group. Most adverse events were mild to moderate in severity. Adverse events in the Psychiatric Disorders, Central Nervous System Disorders and Gastrointestinal Disorders categories were more common with ecopipam than placebo. Notably, more subjects experienced adverse events of somnolence, insomnia, sedation, restlessness, irritability, nausea and vomiting with ecopipam than with placebo. There were no AEs of extra-pyramidal symptoms in the pediatric study. A higher percentage of subjects on ecopipam gained 5 pounds or more during the study than with placebo (17.5% compared to 15%). Orthostatic blood pressure assessments were not done (or not reported). A table of weight changes was provided for the open-label extension study (PSY302A) and almost all of the children gained weight after 3, 6, 9 or 12 months of treatment. Suicidal ideation was seen both during the blinded study as well as the open-label extension study in pediatric subjects ecopipam. There did not appear to be clinically significant ECG findings. However, open-label extension adverse event data have not yet been analyzed.

In the adult study in TS, the most commonly reported adverse events (incidence $\geq 20\%$) were sedation (33%), insomnia (33%), fatigue (33%), somnolence (28%), headache (22%), muscle twitching (22%) and anxiety (22%). Two subjects developed adverse event of akathisia and one developed an adverse event of tremor, both of which are extrapyramidal reactions. Three of 18 subjects (16.7%) also discontinued study drug due to an adverse event.

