For the older obesity and cocaine dependence program, there were subjects who experienced adverse events of weight gain, suicidal ideation, diabetes, extrapyramidal reactions, somnolence, insomnia, hypotension and sexual side effects. There was no raw data on orthostatic blood pressure. In a table of all adverse events during the whole program, the adverse event of dyskinesia is listed but is not in any of the data tables. When reviewing the large Phase 2 and Phase 3 studies in obesity and the other indications, the rate of tardive dyskinesia appears to be extremely low (or absent) and the rate of other extrapyramidal reactions (akathisia, tremor, etc.) appears at rates that are largely less than what is seen with D1/D2 antagonists. Data for shifts in fasting glucose or lipids were not in the Investigator's Brochure prepared by a previous sponsor and comments were made that there were no significant laboratory changes. There did not appear to be a high rate of increased blood glucose or lipids in the adverse event tables for the other studies. Additionally, data on orthostatic blood pressure changes were not documented but no adverse events of orthostatic hypotension were observed.

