12.2.1.3. Other Adverse Event (OAE)

OAEs will be identified by the Drug Safety Physician and if applicable also by the Clinical Study Team Physician during the evaluation of safety data for the Clinical Study Report. Significant adverse events of particular clinical importance, other than SAEs and those AEs leading to discontinuation of the subject/subject from the study, will be classified as OAEs. For each OAE, a narrative may be written and included in the Clinical Study Report. Adverse events of special interest (AESI) include weight gain and extra-pyramidal reactions.

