In this summary, a patient is counted once at the highest grade for which the event occurred in the system organ class and the highest grade for each unique preferred term within that system organ class. Therefore, patients may only contribute once to each preferred term and once to each system organ class. The missing severity grade will be reported in a separate category.

11) Study-treatment-related AEs overall and by system organ class and preferred term.

All those AEs with relationship to treatment marked as "Possibly Related" or "Probably Related" or missing will be reported in the table.

- 12) Study-treatment related AEs by system organ class, preferred term and Highest CTCAE grade
- 13) AEs leading to study treatment termination by system organ class and preferred term.
- 14) AEs leading to study treatment termination by system organ class, preferred term and highest CTCAE grade
- 15) CTCAE Grade 3 or higher AEs, overall and by system organ class and preferred term
- AEs by maximum severity, maximum relatedness and milestones (titration phase, maintenance phase, taper down, and off study drug).

A Serious Adverse Event (SAE) is an AE which falls into one or more of the following categories:

- a. Results in death
- b. Is life-threatening
- c. Requires inpatient hospitalization or prolongation of existing hospitalization
- d. Results in persistent or significant disability or incapacity
- e. Is a congenital anomaly/birth defect
- f. Is any other important medical event

Serious adverse events will be summarized by treatment group and combined over both treatment groups. A summary by age group (children 6-11 and adolescents 12-17) will also be provided.

17) SAEs overall and by system organ class and preferred term.

In this summary, a patient is counted once at the system organ class and once at each preferred term within the system organ class.

Adverse Events of Special Interest (AESI) for ecopipam include Convulsions, Depression and Suicide/Self Injury, Drug Abuse, Dependence and Withdrawal, Dyslipedaemia, Hepatic Disorders, Hyperglycaemia/New Onset Diabetes Mellitus, NMS, and Psychosis and Psychotic Disorders.

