AESI for Parkinsonism include Ataxia, Confusional state, Coordination abnormal, Somnolence, Disturbance in attention, Dyskinesia, Hyperkinesia, Gait disturbance, Memory impairment, Tremor, Vertigo, Agitation, Anxiety, Disturbance in attention, Dystonia, Bradykinesia, Musculoskeletal stiffness, Dysstasia, Gait disturbance, Posture abnormal, Balance disorder, Movement disorder, Movement disorder, Dyskinesia, Muscle rigidity, Coordination abnormal, Muscle contracture, Bradykinesia, Gait disturbance, Terminal insomnia, Nightmare, Poor quality sleep, Sleep disorder, Fatigue, Dizziness, Balance disorder, Restlessness, Amnesia, Confusional state, Dementia, Mental impairment, Speech disorder, Dysphonia, Vocal cord dysfunction, Parosmia, Anosmia, Urinary incontinence, Anxiety, Apathy, Joint stiffness, Reduced facial expression, Confusional state, Flat affect, Constipation, Depression, Dysphagia, Drooling, Fall, Fear of falling, Loss of visual contrast sensitivity, Muscle tightness, Dysgraphia, Dyskinesia, and Weight decreased.

AESI summary tables are listed below:

- 1) AESI for ecopipam overall and by system organ class and preferred term
- 2) AESI for Parkinsonism overall and by system organ class and preferred term.

In this summary, a patient is counted once at the system organ class and once at each preferred term within the system organ class.

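### The two lists of adverse events of special interest in SAP 10.3 have no weight-gain term and no akathisia, so the AESI tables would leave out events that the protocol puts in that class

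*SAP*

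**What the plan says.** Protocol 12.2.1.3 (Other Adverse Event) sets the category: "Adverse events of special interest (AESI) include weight gain and extra-pyramidal reactions". It does not list terms. Protocol 5.3.1 shows what the second class covers. On the adult Tourette study it says: "Two subjects developed adverse event of akathisia and one developed an adverse event of tremor, both of which are extrapyramidal reactions". On the older programme it again gives akathisia as the first example, in the phrase "the rate of other extrapyramidal reactions (akathisia, tremor, etc".

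SAP 10.3 defines AESI through two lists. The first begins "Adverse Events of Special Interest (AESI) for ecopipam include Convulsions, Depression and Suicide/Self Injury, Drug Abuse, Dependence and Withdrawal, Dyslipedaemia, Hepatic Disorders" and ends "Hyperglycaemia/New Onset Diabetes Mellitus, NMS, and Psychosis and Psychotic Disorders". The second begins "AESI for Parkinsonism include Ataxia, Confusional state, Coordination abnormal, Somnolence, Disturbance in attention, Dyskinesia, Hyperkinesia, Gait disturbance, Memory impairment, Tremor, Vertigo" and ends "Dysgraphia, Dyskinesia, and Weight decreased". Two AESI tables follow, one per list, each overall and by system organ class and preferred term. No other AESI output is planned.

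Elsewhere, SAP 10.3 tabulates all adverse events by arm, system organ class and preferred term. SAP 10.5 summarises weight, change in weight and gain of at least 7%. SAP 10.9.2 summarises BARS scores by arm and visit.

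**The concern.** The protocol names two classes of special interest. The SAP carries one of them only in part and the other not at all. A reader who goes to the AESI tables for the protocol's own categories would find no row for weight gain and none for akathisia, and could take that silence as absence of events.

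This matters because both classes bear on the case made for the drug. Protocol 5.3.2 and 5.3.3 expect fewer extrapyramidal reactions and a lighter metabolic burden than with current dopamine antagonists. The AESI tables are a natural place to look for evidence on that, and they should group reported events as the protocol does.

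A second matter is how the Parkinsonism table will be read. Its list mixes motor terms with somnolence, fatigue, anxiety, depression, dizziness, constipation and sleep terms, so its overall row is not a count of motor events.

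**Working it through.** No figure in the plan is at issue. The check sets the protocol's categories against the SAP's lists and counts terms.

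**1. Size of the lists.** The ecopipam list has 8 topics, reading drug abuse, dependence and withdrawal as one. The Parkinsonism list has 64 entries. Three terms appear three times (Confusional state, Dyskinesia, Gait disturbance). Six appear twice (Coordination abnormal, Disturbance in attention, Anxiety, Bradykinesia, Balance disorder, Movement disorder). Surplus entries: 3 × 2 + 6 × 1 = 12. Distinct terms: 64 − 12 = 52.

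**2. Search for the protocol's classes.**

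| Sought | Ecopipam list | Parkinsonism list | Shown elsewhere in the SAP |
|---|---|---|---|
| Weight gain | none | none; only Weight decreased | 10.3 general AE tables; 10.5 weight change and gain ≥7% |
| Akathisia | none | none; Restlessness is listed | 10.3 general AE tables; 10.9.2 BARS |
| Extra-pyramidal reactions as a named group | none | none | none |
| Individual extra-pyramidal terms | none listed as such | Tremor, Dystonia, Bradykinesia, Dyskinesia, Muscle rigidity | 10.3 general AE tables; 10.9.1 AIMS |

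Restlessness does not fill the akathisia gap, because the tables work by preferred term and an event coded as akathisia would not fall on that row.

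**3. What the gap would have meant in earlier data.** In the adult Tourette study (Protocol 5.3.1), akathisia was reported in 2 of 18 subjects (2/18 = 11%) and tremor in 1 of 18 (1/18 = 6%). Of these three reports, the SAP lists would have placed one, the tremor, in an AESI table. In the paediatric Tourette study (same section), a gain of 5 pounds or more was seen in 17.5% on ecopipam and 15% on placebo. With 40 subjects per treatment in that crossover, this is 0.175 × 40 = 7 against 0.15 × 40 = 6. The second comparison shows that weight was being watched, not that an effect exists.

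**4. The pooled Parkinsonism total.** In the Phase 3 obesity studies (Protocol 5.2.2.1), ecopipam rates were depression 16% (236/1482), somnolence 15% (216/1482) and anxiety 14% (211/1482), each about twice the placebo frequency. All three terms are in the Parkinsonism list. A difference in its overall row could therefore arise with no motor event behind it. Fatigue (15%, 215/1482) is also listed, but the protocol says it was similar on placebo, so those data give no reason to expect it to drive a difference.

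**The case against.** The strongest reply is that no safety information is lost. Every reported event, including akathisia and weight gain, appears by arm in the general preferred-term table of SAP 10.3, and further tables repeat this by region, weight band, study phase and grade. Measured weight and BARS are summarised by visit. On the metabolic side, the ecopipam list includes dyslipidaemia and hyperglycaemia, and SAP 10.4 gives special attention to glucose and lipids. All of this stands. A reader might infer that the trial could not show an imbalance in weight gain or akathisia; the documents do not support that. Only the AESI tables are affected.

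It can also be said that both documents use the word include, and that the protocol names a class without naming akathisia in its AESI sentence. The first point does not close the gap, because the tables can be built only from what the lists contain. The second is met by Protocol 5.3.1, which assigns akathisia to the class. But it would be too strong to infer that the SAP drops extra-pyramidal reactions altogether, since the Parkinsonism list holds many of them.

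Three further inferences are tempting and go too far.

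- That the Parkinsonism table will give a false signal. Its rows are by preferred term, so somnolence or anxiety would be seen as such, and only pooled totals are diluted. The obesity rates come from adults treated for 52 weeks, the akathisia rate from an uncontrolled study, and the paediatric Tourette study had no extra-pyramidal adverse events.
- That Weight decreased is a slip for weight increased. It sits in a separately titled list, and Protocol 5.2.2.1 reports dose-dependent weight loss, so it may be there on purpose.
- That SAP Section 12, which declares no changes, is false on this account. Protocol 13.2.2 plans no AESI analysis, so the AESI tables are additions and replace no planned analysis.

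**Conclusion.** The mismatch is real and small. Of the two classes the protocol names, weight gain is missing from the AESI lists and extra-pyramidal reactions are covered in part, without akathisia. The effect is confined to two tables. No efficacy result changes, and the underlying events stay visible in other outputs. The correction is still worth making, because the SAP should carry the protocol's own definition and the AESI tables are where a reader will look for it.

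The conclusion rests on two assumptions. The lists printed in SAP 10.3 are taken as the operative ones. The eight ecopipam topics are given by title only, so it is also assumed that no term set behind them brings in weight gain or akathisia. If one did, such events would be counted under a different topic and still not as the protocol's category.

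The pooled Parkinsonism total should not be interpreted as a motor outcome. That is a caution about reading the table and does not make the list an error.

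**What to change.** Before unblinding, amend SAP 10.3 in two places:

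1. Add a weight-gain AESI group, with weight increased and related preferred terms written out.
2. Add an extra-pyramidal AESI group made up of akathisia and the extra-pyramidal terms already in the Parkinsonism list, with its own table by arm, system organ class and preferred term.

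Add a footnote to the Parkinsonism table saying that its total includes non-motor terms. Removing the 12 repeated entries is tidying. Separating motor from non-motor terms, or taking out Weight decreased, is optional and a matter of preference.

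The cost is an edit to the term lists and the matching table shells. No new data, visits or protocol amendment are needed. Fixing the terms while the data are blinded also means that the grouping cannot be influenced by the results.

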10.4. Laboratory Evaluations

Blood samples for hematology, biochemistry, and urine samples for urinalysis are to be collected at screening, Baseline, Weeks 12 and 7 day and 14 day Follow Up visits. All results will be provided using International System of Units (SI). HbA1c will be measured at the baseline and completion/early termination visits.

Descriptive statistics for hematology, biochemistry and HbA1c will be provided for each test parameter and for change from baseline treatment by visit and for each treatment group (specific emphasis will be placed on mean changes between ecopipam and placebo in fasting glucose levels and blood lipid parameters). Shift tables (i.e., low-normal-high at Baseline versus low-normal-high at each post-baseline visit in a 3-by-3 contingency table) will be provided for hematology, biochemistry, HbA1c and urine to assess changes from Baseline in laboratory values by visit for each treatment group.

Separate listings will be provided for all laboratory evaluations (hematology, biochemistry, HbA1c and urinalysis.

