5.3.2. Assessment of Benefit

A review of the efficacy evaluations for ecopipam in the two studies conducted in subjects with TS reveals improvement on the YGTSS scores and other measures of illness severity from baseline to end point.

In a Phase 2a, open-label, non-randomized study (PSY301), the activity and safety of ecopipam in 18 adult subjects with TS was evaluated. Subjects were to receive ecopipam HCl 50 mg for 2 weeks followed by 100 mg for 6 weeks. The primary outcome measure was the YGTSS Total (MP) score. After ecopipam treatment, the YGTSS Total score, motor tics score, phonic tics score and overall impairment decreased from baseline to endpoint, suggesting that the severity of tics was decreased (Table 16, Investigator's Brochure).

In a Phase 2b double-blind, randomized crossover study in children/adolescents (ages 7-17 years) with TS (PSY302), 40 subjects were enrolled and 38 (95.0%) completed the study. The primary endpoint was the YGTSS Total (MP) score.

Ecopipam treatment resulted in a numerical decrease in the YGTSS Total score relative to the placebo treatment, but the decrease was not statistically significant (Figure 9, Investigator's Brochure). The least squares means (\pm SE) of the difference between ecopipam and placebo treatment were -2.8885 (\pm 1.5282); 95% CI: -5.9822, 0.2053, p=0.0664) on Day 16 and -2.1366 (\pm 1.6551; 95% CI: -5.4871, 1.2139, p=0.2045) on Day 30.

Based on the available safety data, there are some safety advantages for ecopipam compared to D2 antagonists, but the full measure of differentiation will not be known until after a larger and longer Phase 3 program. The rate of tardive dyskinesia and other extrapyramidal reactions commonly associated with D2 antagonists appears much lower with ecopipam. Other possible advantages include a decreased risk of lipid changes, hyperglycemia and orthostatic hypotension.

An individual subject may not receive any therapeutic benefit from participating in an investigational study however, by contributing to medical research, others will be helped. All subjects participating in the study will receive physical examinations, various laboratory tests, ECGs and a systematic evaluation of their condition. Ecopipam may help improve symptoms for participants.

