3.5. Determination of Sample Size

A sample size of 75 subjects per group will provide >80% power to detect difference between groups of 3 points on change from baseline the Yale Global Tic Severity Scale-Total Tic Score (YGTSS-TTS), with standard deviation = 6.1 and alpha = 0.05, assuming 10% drop out.

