3.6. Treatment Assignment & Blinding

Subjects will be randomized 1:1 to either ecopipam or matching placebo. Randomization will be stratified by weight band (\geq 18 to \leq 23 kg, >23 to \leq 34 kg, >34 to \leq 44 kg, >44 to \leq 68 kg, >68 to \leq 83 kg, >83 kg).

Throughout the study, subjects and all personnel involved with the conduct and interpretation of the study, including the subject, parents/guardians, investigators, site personnel, and sponsor staff will be blinded to the treatment codes. Randomization data will be kept strictly confidential, filed securely by an appropriate group with the Sponsor or Syneos and accessible only to authorized persons (e.g., Safety) until the time of unblinding.

A master list of all treatments and the subject numbers associated with them will be maintained electronically by the unblinded clinical supply vendor and the unblinded personnel at Syneos. The process to request unblinding and the randomization code will be outlined in a separate document. The site will be trained in this process and it should be used only in an emergency. These codes should only be broken if knowledge of the subject's randomization code will affect his/her medical treatment. If possible, before breaking the blind, the Investigator should consult with the Sponsor to ascertain the necessity of breaking the code. The Investigator is to record the date and time of requesting the code and the reason for breaking the code.

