6.1. General Methods

All analyses and outputs will be produced using SAS[®] version 9.4 or later. Unless otherwise specified, efficacy and safety summaries will be presented for each treatment. All other summaries will be presented for each treatment and overall. Continuous variables will be summarized using the number of observations (n), mean, standard deviation (SD), median, minimum, and maximum. Categorical variables will be summarized using number of observations (n), frequency, and percentages of subjects.

All relevant subject data will be included in listings. All randomized subjects entered into the database will be included in subject data listings. All by visit summaries will use the nominal visit. Unscheduled visits will not be summarized but will be included in the listings.

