10.10. COVID-19 Analyses

Due to COVID-19 pandemic, additional analyses will be conducted:

- Listings of COVID-19 related study disruptions by subject and by site, including descriptions of the disruption.
- The amount of missing data by treatment group and overall by endpoint for data missing due to COVID-19 will be summarized in a table.
- Protocol deviations due to COVID-19 will be summarized by type and treatment in a table.

11. Interim Analyses

An unblinded interim analysis will be conducted when approximately 50% of the 150 planned subjects have been randomized (1:1 ratio between ecopipam and placebo) and completed treatment or are terminated early. The interim analysis will be performed by an independent statistician and governed by an external Data Safety Monitoring Board (DSMB). The conditional power will be calculated to help the DSMB assess the probability of a successful study based on observed data.

The primary efficacy endpoint of the study is the YGTSS-TTS. A smaller YGTSS-TTS score indicates a better condition in subjects with Tourette's syndrome, and we may expect that the ecopipam group has a larger reduction than the placebo group. Let μ_{σ} be the mean change YGTSS-TTS score from Baseline to Week 12 for the ecopipam group, and μ_p be the mean change YGTSS-TTS score from Baseline to Week 12 for the placebo group. Then, given $H_0: \mu_{\sigma} \ge \mu_p \equiv \Delta_{\sigma-p} \ge 0$ vs. $H_1: \mu_{\sigma} < \mu_p \equiv \Delta_{\sigma-p} < 0$. Since the original sample size calculation is based on two-sided test at a significance level of α =5%, we will use $\alpha/2$ =2.5% to match the one-sided test.

The primary endpoint will be analyzed with a Mixed Model for Repeated Measures (MMRM) model using the SAS MIXED procedure with REPEATED statement. The model will include fixed effects for treatment, visit, visit interaction between treatment and visit, region, age group (0 = children 6-11, 1 = adolescents 12-17) and covariate for baseline YGTSS-TTS.

To determine if the total sample size should be increased from N (to N^*), the conditional power based on the MMRM will be calculated at the interim analysis using the observed effects (where n=75) and the planned sample size (N=150).

If it is determined that the sample size should be increased, the CHW (Cui-Hung-Wang) statistic, which controls the type I error, will be used. The CHW statistic is a weighted statistic defined as:

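### SAP 10.4 emphasises an ecopipam-versus-placebo comparison of fasting glucose and lipids but plans no between-arm difference, confidence interval or baseline-adjusted estimate (low priority)

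*SAP*

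**What the plan says.** SAP 10.4 plans descriptive statistics for each hematology and biochemistry parameter and for HbA1c, "for change from baseline treatment by visit and for each treatment group". Inside that sentence, in parentheses, it adds that "specific emphasis will be placed on mean changes between ecopipam and placebo in fasting glucose levels and blood lipid parameters". It also plans shift tables (low, normal or high at Baseline against each later visit) per arm, and listings.

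SAP 6.1 defines what a descriptive summary contains: "Continuous variables will be summarized using the number of observations (n), mean, standard deviation (SD), median, minimum, and maximum". SAP 10 and Protocol 13.2.2 say only that laboratory data are summarised by treatment and visit. SAP 10.3 counts dyslipidaemia and hyperglycaemia or new-onset diabetes among the adverse events of special interest, again by treatment group.

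Models with a baseline covariate appear only for efficacy endpoints (SAP 8.1 and 8.2). Neither document specifies a between-arm difference, an interval or a baseline-adjusted model for a laboratory parameter.

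**The concern.** A mean change between ecopipam and placebo is a between-arm quantity, and SAP 10.4 picks it out of all the laboratory comparisons for emphasis. The method attached to it stops at one row per arm. The report as planned would therefore show two means side by side, without the difference between them or the range of differences compatible with the data.

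What is at stake is modest. The emphasised comparison would reach the report without a stated precision, and the choice of contrast and model would be left until after the data are seen. The Baseline value, already collected, would not be used as a covariate, so some precision available at no cost in subjects or procedures would be given up.

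**Working it through.** **The plan's own figure.** The only precision statement in the documents is for the primary endpoint: "A sample size of 75 subjects per group will provide >80% power to detect difference between groups of 3 points", "with standard deviation = 6.1 and alpha = 0.05, assuming 10% drop out" (SAP 3.5). Allocation is 1:1 (SAP 3.6) and the calculation is two-sided (SAP 11). Taking 10% off 75 leaves 67.5 per arm.

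- SE = 6.1 × sqrt(2/67.5) = 1.05, and 3/1.05 = 2.857.
- Power = Φ(2.857 − 1.960) = 81.5%. The noncentral t gives 80.7% to 81.2% at 67 to 68 per arm.
- Conversely, 65 per arm are required, and 65/0.9 rounds up to 73, against 75 planned.

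The stated power reproduces. It supplies the number of subjects for what follows and has no other bearing on the point.

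**What the planned tables allow.** From n, mean and SD of change in each arm:

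- difference = mean(ecopipam) − mean(placebo)
- SE = sqrt(SD_e²/n_e + SD_p²/n_p)

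With 67 per arm, the 95% half-width is t(0.975, 132) × sqrt(2/67) = 0.34 SD of change (0.32 with all 75). The difference detectable with 80% power is (1.960 + 0.842) × sqrt(2/67) = 0.48 SD of change. An interval at this sample size is therefore feasible and informative.

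The adjusted difference also needs the within-arm covariance of the Baseline and Week 12 values in the same subjects, which is not a planned output. It could be backed out of the SDs of Baseline, Week 12 and change only if all three were computed on the same subjects, and the SAP does not say that they will be.

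**Gain from adjustment.** The documents give neither an SD nor a baseline to Week 12 correlation (r) for glucose or lipids. I therefore work in units of the single-visit SD, assume equal SDs at the two visits, and vary r. I ignore the one degree of freedom spent on the covariate.

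- Unadjusted change: half-width = 0.3418 × sqrt(2(1 − r))
- ANCOVA: half-width = 0.3418 × sqrt(1 − r²)
- Ratio = sqrt((1 + r)/2)

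| r (assumed) | Change | ANCOVA | Ratio | Shorter by |
|---|---|---|---|---|
| 0.3 | 0.40 | 0.33 | 0.81 | 19% |
| 0.4 | 0.37 | 0.31 | 0.84 | 16% |
| 0.5 | 0.34 | 0.30 | 0.87 | 13% |
| 0.7 | 0.26 | 0.24 | 0.92 | 8% |
| 0.8 | 0.22 | 0.21 | 0.95 | 5% |

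**Chance baseline imbalance.** With 67.5 per arm, a Baseline difference above 0.2 SD in either direction has probability 2 × (1 − Φ(0.2/sqrt(2/67.5))) = 0.245. Given such an imbalance, the change-score difference departs from the adjusted one by (1 − r) times the imbalance, with opposite sign. At r = 0.4 that is at least 0.6 × 0.2 = 0.12 SD. The SE of the change-score difference at r = 0.4 is sqrt(1.2) × sqrt(2/67.5) = 0.19 SD, so 0.12 lies within one SE.

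This is not a second effect. The change-score variance factor splits as 2(1 − r) = (1 − r²) + (1 − r)². The first term is the ANCOVA variance and the second is the imbalance contribution. The table already counts it.

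**The case against.** The strongest reply is that descriptive-only laboratory reporting is common, that the protocol prespecifies it, and that the parenthesis sits in a sentence about descriptive statistics. It may mean no more than that these tables will be displayed prominently. No hypothesis, decision rule or sample size depends on the comparison. That stands, and it sets the priority low. It does not remove the gap: a comparison chosen for emphasis still has no comparative output.

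Three stronger readings are tempting, and the documents do not support them.

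- **That the report could not say how large a glucose or lipid rise is excluded.** It could be worked out, unadjusted, from the six per-arm numbers. It is simply not planned, and the adjusted version is not supplied.
- **That the plan ignores Baseline.** Change from baseline and the shift tables both use it. What is missing is Baseline as a covariate. Nor does chance imbalance bias the comparison: under randomisation the unadjusted difference is unbiased on average, and the imbalance is part of its sampling error.
- **That the trial is meant to demonstrate a metabolic advantage.** Protocol 5.3.2 does say "Other possible advantages include a decreased risk of lipid changes, hyperglycemia and orthostatic hypotension", but that paragraph compares ecopipam with D2 antagonists. This trial has no such arm, and a placebo contrast cannot test that advantage. The point rests on SAP 10.4 alone.

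**Conclusion.** The point holds in a limited form. SAP 10.4 announces an emphasis on the ecopipam-versus-placebo contrast in fasting glucose and lipids and specifies only per-arm output. The unadjusted contrast can be derived by a reader, whereas the more precise baseline-adjusted one is not provided.

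The gain in precision is a 95% interval shorter by about 19% to 5%, for assumed correlations of 0.3 to 0.8, about 67 subjects per arm and equal SDs at the two visits. The higher the true correlation, the smaller the gain. The primary conclusion, the type I error and the sample size are all unaffected. This is a low-priority reporting improvement.

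**What to change.** In SAP 10.4, for fasting glucose, cholesterol and triglycerides (HbA1c optional), add the ecopipam minus placebo difference at Week 12 with a 95% CI, from an ANCOVA of the Week 12 value on treatment and the Baseline value. Week 12 is the only scheduled laboratory visit between Baseline and the post-treatment follow-up visits, so one model per analyte is enough.

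Use scheduled Week 12 samples and state how early-termination samples are handled. The schedule of assessments puts completion and early termination in one column, and SAP 6.4 applies no visit windows, so this has to be written down. Label the results descriptive, give no p-value, and keep the existing summaries, shift tables and listings.

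The cost is three or four short models on data already collected, with no new procedures or subjects. The downside is several intervals not adjusted for multiplicity, which must be read as descriptive.
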